4.1 Primary Outcomes

All Studies

The primary analyses will compare: (1) PlayMed vs OP; and (2) PlayMed vs control guidelines on their mean/median: (i) MCQ score, and (ii) OSCE scores. Comparisons will be made using an unpaired t-test or a Mann-Whitney test for parametric and non-parametric data, respectively. P-values <0.05 will be considered statistically significant.

Effect sizes for will be calculated using Cohen's d (d) with 95% confidence intervals (95%CI) using the 'effsize' package.⁷ Effect sizes will be considered small if $0.2 \leq d < 0.5$, medium if $0.5 \leq d < 0.8$, and large if $d \geq 0.8$.

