2.1 Lay Summary & Aims

Medicine has traditionally been learned through the face-to-face lecture, clinical experience on hospital wards, and student self-direction to additional resources such as textbooks and clinical guidelines. Recently educators have sought to improve student learning by providing adjuncts to these methods. The rapid development of computerized technology has seen the emergence of online educational packages in medical programs throughout the world.

‘PlayMed’ is a serious computer game that has been developed to teach paediatrics to medical students. It allows students to learn and apply clinical algorithms for managing patients in a safe, simulated environment. Preliminary data gained from a pilot study suggests that PlayMed improved students’ knowledge of asthma management. However, the efficacy of PlayMed as a learning tool has not been tested against alternative online educational tools, therefore we propose to conduct a randomized control trial of PlayMed using an online educational package as a control. Furthermore, we aim to assess the utility of PlayMed in different populations including nurses and doctors.

We have targeted two common and important paediatric clinical presentations (asthma and seizures) as the focus of our teaching and assessment in this study. It is likely that students will be exposed to both of these conditions during their clinical attachments; the acute management of both conditions is outlined in current NSW Health Paediatric Clinical Practice Guidelines (CPG); and both asthma and seizure disorders are listed in the Australian Curriculum Framework For Junior Doctors. The current UNSW Phase 3 Children’s Health course includes one lecture on each clinical problem.

Under the “G4MER” Program, we plan to perform a series of randomised control trials to see if PlayMed is an effective teaching adjunct to our standard course(s), and if this game is more effective than other online packages for medical students, doctors and nurses. We hypothesise that participants exposed to the game (in addition to standard teaching) will demonstrate superior knowledge and clinical skills compared to those exposed to the alternative online packages, and to those who only receive standard teaching. Additionally, we hypothesise that increased time spent playing the game will improve performance in knowledge-based and clinical assessments.

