3.6 Assessment & Outcomes Measures

Studies 1A and 2A

Participants will be assessed for:

1. Primary outcomes

- Knowledge acquisition
 - Participant knowledge will be assessed using a 10-point single-best option multiple-choice questionnaire (MCQ); correct answers, with an explanation, will be provided to all participants at the end of the study via email.
- Clinical performance
 - Participant clinical skills will be assessed via an observed structured clinical examination (OSCE) administered in the simulation laboratory (immediately after the knowledge test); participants will be tested across two clinical scenarios. Strict marking criteria will be used to ensure standardisation, with a total possible maximum score of 30. Individual feedback will be provided by assessors immediately after each scenario.

2. Secondary outcomes

- Educational experience
 - Participants will be asked to complete a short survey using 5-point Likert scale (strongly agree, agree, neutral, disagree, strongly disagree). Students will be asked for comments (free text responses) regarding their engagement with, and perception of the educational value, of the learning tool.

The time commitment required of participants for assessment will be approximately 60 mins.

Studies 1B and 2B

Participants will be assessed for:

1. Primary outcomes

- Knowledge acquisition
 - Participant knowledge will be assessed using a 15-point single-best option MCQ; correct answers, with an explanation, will be provided to all participants at the end of the study via email.
- Clinical performance
 - Participant clinical skills will be assessed via an OSCE administered in the simulation laboratory (immediately after the knowledge test); participants will be tested across two clinical scenarios. Strict marking criteria will be used to ensure standardisation, with a total possible maximum score of 50. Individual feedback will be provided by assessors at the conclusion of the OSCE portion of the assessment.

2. Secondary outcomes

- Educational experience
 - Participants will be asked to complete a short survey using 5-point Likert scale (strongly agree, agree, neutral, disagree, strongly disagree). Students

will be asked for comments (free text responses) regarding their engagement with, and perception of the educational value, of the learning tool.

- Future impact on clinical practice

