3.7 Sample Size

Study 1A

GLIMMPSE (<http://glimmpse.samplesizeshop.org/#/>) was utilised for sample size calculation with equal group sizes (i.e ratio of groups 1:1:1). In our initial pilot study, the mean quiz scores were 7.0 (SD 1.4) and 6.0 (SD 1.4) for the PlayMed and control cohorts (standard teaching only) respectively.⁶ If we assume that students in the OP cohort will achieve quiz scores of 50% the difference between PlayMed and controls (i.e. score of 6.5), then the following sample size is required:

- A total of 54 subjects (i.e. 18 in each group) to be able to reject the null hypothesis that the population means of the experimental and control groups are equal with probability (power) 0.8. The Type I error probability associated with this test of this null hypothesis is 0.05.
- Assuming a total drop-out rate of 20%, we will recruit 22 subjects for each group, i.e. 18 PlayMed, 18 OP and 18 controls.

Study 2A

Given we have no preliminary data for doctors and nurses, the same sample size estimate will be used for this study. We will recruit 22 subjects for each group, i.e. 22 PlayMed, 22 OP and 22 controls.

Studies 1B and 2B

The same sample size estimates will be utilised for these studies. For each study we will recruit 22 subjects for each group, i.e. 22 PlayMed, 22 OP and 22 controls.

4. Statistical Analysis Plan (SAP)

All Studies

Descriptive and inferential statistics will be used. Normally distributed data will be presented by mean and standard deviation (SD) and non-normally distributed data will be presented by median and interquartile range (IQR). Binary and categorical data will be presented using counts and percentages. R v3.4.4 will be used for all statistical analyses.

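### Cohen's d, with its SD unstated, is the only between-arm estimate given a confidence interval, and in the staff studies any doctor/nurse spread enters it unadjusted

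*Combined protocol and SAP*

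**What the plan says.** Section 4.1 applies to all four studies. It sets two pairwise contrasts on two scores: "The primary analyses will compare: (1) PlayMed vs OP; and (2) PlayMed vs control guidelines on their mean/median: (i) MCQ score, and (ii) OSCE scores". The tests are two-sample tests: "Comparisons will be made using an unpaired t-test or a Mann-Whitney test for parametric and non-parametric data, respectively". The effect measure follows: "Effect sizes for will be calculated using Cohen's d (d) with 95% confidence intervals (95%CI". Bands are then fixed for d (small from 0.2, medium from 0.5, large from 0.8), the same for every study and outcome.

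The opening of section 4 adds summaries by group: "Normally distributed data will be presented by mean and standard deviation (SD) and non-normally distributed data will be presented by median and interquartile range (IQR". Nothing in section 4 plans a difference in means, a difference in medians or a location shift with an interval. Nothing says whether d is divided by the SD of the two arms compared, of all three arms, or of the comparator arm.

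Section 2.1 gives one purpose of the programme: "we aim to assess the utility of PlayMed in different populations including nurses and doctors". Section 3.2 admits both doctors and nurses to Studies 1B and 2B. Section 3.4 plans a doctor/nurse stratum for staff but places it in Studies 2A and 2B, although 2A enrols students. Section 4.1 does not mention job. In section 3.6 the student tests are out of 10 (MCQ) and 30 (OSCE). The staff MCQ is out of 15, and the staff OSCE is marked "with a total possible maximum score of 50".

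**The concern.** The trial asks how much better participants score after the game. A reader would want that in marks, with an interval. The plan gives it only in SD units, from an unnamed SD, with a verbal label attached.

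In the staff studies this matters more. If doctors and nurses differ in average score, the pooled SD contains that difference as well as ordinary variation between people in the same job. Two things follow:

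- d falls for an unchanged gain in marks.
- The unadjusted test and interval carry error that a term for job would remove. Where allocation was stratified by job, the unadjusted standard error is also too large for the design.

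PlayMed could then be labelled less effective in staff, or missed, because two professions were pooled.

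**Working it through.** **Inputs from the documents.** Section 3.7 gives pilot student MCQ means of 7.0 and 6.0, an SD of 1.4 in both groups, an assumed OP mean of 6.5 and 18 evaluable per arm. Section 3.6 gives the student MCQ maximum of 10. Section 3.7 also says, under its Study 2A heading, that there are no preliminary data on doctors and nurses. No SD is given for any OSCE.

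**Assumptions.** The within-job SD in staff equals the student pilot SD in percent of maximum (1.4/10 = 14 points). Staff are half doctors and half nurses. The job gap is varied over 0, 20 and 30 percentage points. None of these has a source in the documents.

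**Step 1: what the planning inputs imply.** The plan states no target d. Its inputs give 1.0/1.4 = 0.71 for PlayMed vs control and 0.5/1.4 = 0.36 for PlayMed vs OP. In percent of maximum the first is 10/14 = 0.71.

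**Step 2: staff denominator.** With share p of doctors, total SD = sqrt(within-job SD² + p(1−p) × gap²). At p = 0.5 the second term is (gap/2)².

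| Assumed job gap | Total SD | d for a 10-point gain |
|---|---|---|
| 0 | 14.0 | 10/14.0 = 0.71 |
| 20 | sqrt(196 + 100) = 17.2 | 10/17.2 = 0.58 |
| 30 | sqrt(196 + 225) = 20.5 | 10/20.5 = 0.49 |

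The label moves from medium to small only when total SD exceeds 10/0.5 = 20, that is, when the gap exceeds 2 × sqrt(400 − 196) = 28.6 points. A less even mix weakens the effect: at 25:75 and a 20-point gap, total SD is sqrt(196 + 0.1875 × 400) = 16.5 and d = 0.61.

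**Step 3: error of the unadjusted comparison, 18 per arm, 20-point gap.** If job is balanced across arms by stratification, the job gap cancels from the mean difference. The true standard error is 14 × sqrt(2/18) = 4.67 points. The two-sample test instead estimates 17.2 × sqrt(2/18) = 5.73, which is 17.2/14 = 1.23 times as large. With t = 2.03 on 34 df, the 95% half-width is about 11.7 points where about 9.5 would do. In simulation under these assumptions, with a true 10-point gain, the nominal 95% unadjusted interval covers about 98% of the time. Power is about 36% unadjusted and 55% with job in a three-arm model.

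If a staff study is not stratified by job, as section 3.4 reads for 1B, coverage is close to nominal, because chance imbalance in job adds to the true error. The interval is still wider than one adjusted for job.

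**Step 4: what the missing interval would look like.** For the student MCQ with SD 1.4, the half-width is 2.03 × 1.4 × sqrt(2/18) = 0.95 points at 18 per arm. Against the planning difference of 1.0 point, this is directly readable in a way that d is not.

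**The case against.** The strongest reply is that this is a modest reporting gap. Two-sample tests with d are a legitimate choice. Section 4 promises means and SDs by group, so a reader can compute a mean difference and its unadjusted interval when data are treated as normal. That stands in part. It fails for outcomes summarised as median and IQR, and it cannot recover an estimate adjusted for job.

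The job gaps are also assumptions. That stands fully: if doctors and nurses score alike, the staff effect vanishes.

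A reader might infer three stronger points that the documents do not support:

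- **That d uses each pair's own SD, so equal gains get different effect sizes in the two contrasts.** The denominator is not stated, and the only SDs given are 1.4 and 1.4, which imply no systematic difference. Noise in the means swamps any noise in the SD: simulating a true difference of 1.0 in both contrasts, SD 1.4 and 18 per arm, the two labels disagree in 54.7% of trials with pair SDs and 54.0% with a three-arm SD.
- **That the different maxima for students and staff change d.** If the SD scales with the maximum, 1/1.4 and 1.5/2.1 both equal 0.71.
- **That percent of maximum would make student and staff results directly comparable.** The tests may differ in difficulty, and the plan describes no student-staff comparison.

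Small-sample bias in d is about 2% at 34 df (0.714 becomes 0.698), which is too small to matter here.

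**Conclusion.** The point holds in a limited form. Section 4.1 gives a confidence interval only to a standardised effect whose SD is unnamed, and it plans no score difference with an interval. In the staff studies it leaves job out of the analysis although section 3.4 anticipates stratifying on it.

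The omission of the interval and of the SD is a matter of record. The staff effect is conditional: at a 20-point job gap with an even mix and a 14-point within-job SD, d falls from 0.71 to 0.58 (still medium) and power from about 55% to 36%. At 30 points d is 0.49 (small). With no gap there is no loss. The planned tests are not invalid: under stratified allocation the unadjusted intervals err on the wide side. The change is worth making because it is cheap and the effect estimate is what readers will use.

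**What to change.** In section 4.1:

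- For each outcome, fit one linear model with three arms. Report PlayMed minus OP and PlayMed minus control as mean differences with 95% CIs, in score points and in percent of maximum.
- In Studies 1B and 2B, include job (doctor/nurse) as a term.
- Keep d as a supplement, name its SD, and use the model's residual SD for both contrasts. A small-sample correction is optional.
- Say whether the p-value comes from this model or from the planned two-sample test, since the two can differ in staff.

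In section 3.4, reconcile the studies named for the job stratum (2A and 2B) with the staff studies (1B and 2B).

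The cost is SAP wording, a few lines of R and the assumption of a common variance across arms, which should be checked on these short bounded scores. No new data are needed beyond each staff member's job. The change does not address the mean imputation in section 4.3, which would still make the residual SD and the intervals too small; that is a separate matter.

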4.2. Secondary Outcomes

All Studies

Descriptive statistics will be used to explore Likert scale data and reported as percentage of participants who “strongly agree”, “agree”, “neutral”, “disagree”, or “strongly disagree”.

Qualitative data will be explored thematically using a document analysis approach. Data will be manually transcribed into NVIVO™ which will assist with data immersion. Labels will be created and assigned to text, which describe key meanings and ideas; with each successive pass codes will move from descriptive to interpretive as key themes are identified.

4.3 Missing Data

The primary analyses will be performed using a modified intention-to-treat (ITT) basis. For participants who are randomised and do not attend for assessment, a mean imputation of the assessment scores from their allocation group will used. A sensitivity, per-protocol analysis will also be performed, with no restrictions placed on the minimum time spent using the allocated intervention.

5. Informed Consent Forms (ICF)

Studies 1A and 2A

Written consent will be gained from the Medical students using the consent forms attached to the application.

Studies 1B and 2B

Written consent will be gained from the medical and nursing staff using the consent forms attached to the application.

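### Filling in absent participants with their own arm's mean in the primary analysis raises the type I error of the nominal 5% t-test to about 11% at the planned attrition

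*Combined protocol and SAP*

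**What the plan says.** Section 4.3 (Missing Data) sets the primary analysis population: "The primary analyses will be performed using a modified intention-to-treat (ITT) basis". For anyone randomised who is not assessed, "a mean imputation of the assessment scores from their allocation group will used". The one sensitivity analysis is described as follows: "A sensitivity, per-protocol analysis will also be performed, with no restrictions placed on the minimum time spent using the allocated intervention".

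Section 4.1 gives the test: "Comparisons will be made using an unpaired t-test or a Mann-Whitney test for parametric and non-parametric data, respectively". It gives the threshold as "P-values <0.05 will be considered statistically significant", and adds Cohen's d with a 95% confidence interval, labelled large from 0.8 upwards.

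Section 3.7 gives the expected attrition: "Assuming a total drop-out rate of 20%, we will recruit 22 subjects for each group". The evaluable number is "A total of 54 subjects (i.e. 18 in each group").

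The plan contains no variance or degrees-of-freedom correction, no multiple imputation, and no stated assumption about why scores are missing.

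**The concern.** A value set equal to the arm's observed mean carries no information about the person who was absent. It cannot move the estimated difference, and it contributes zero to the within-arm sum of squares. It does raise the sample size and the degrees of freedom that the test uses. The analysis therefore reports more precision than the data hold, and the overstatement grows with the number absent.

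The primary p-values, the confidence intervals and Cohen's d are all affected wherever a compared arm has absentees. Section 2.2 says the trial is meant to show whether further investment in the game is worthwhile. An excess of false positives and overstated effect sizes bear directly on that decision.

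**Working it through.** **Inputs.** Randomised per arm n = 22, assessed per arm m = 18, and quiz-score SD 1.4 with means 7.0 and 6.0 (all section 3.7). Threshold 0.05 (section 4.1), taken as two-sided because the plan does not say.

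**The plan's own figures.** Adding 20% to 18 gives 18 × 1.2 = 21.6, or 22, which matches the recruitment figure; dividing by 0.8 gives 22.5, or 23. Losing 4 of 22 is 18.2%. The 18 per group itself is not reproduced by a two-sided t-test of a 1-point difference with SD 1.4, which needs 32 per arm. That is a separate matter: the error rates below depend only on n, m and the threshold.

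**Effect on the t statistic.** Let SS be the within-arm sum of squares pooled over two arms of equal size.

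- Attendees only: SE² = [SS / (2(m − 1))] × (2/m) = SS / [m(m − 1)]
- After imputation: SS and the mean difference are unchanged, so SE² = SS / [n(n − 1)]
- Ratio of t statistics: √[n(n − 1) / (m(m − 1))] = √[(22 × 21) / (18 × 17)] = √(462/306) = 1.229

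**True type I error.** The imputed t is compared with the critical value on 2n − 2 = 42 df, which is 2.018. The underlying statistic has 2m − 2 = 34 df. The test therefore rejects when |T₃₄| > 2.018/1.229 = 1.642, which has probability 0.1097. Coverage of the nominal 95% interval for the difference is 1 − 0.1097 = 0.89.

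**Cohen's d.** The SD shrinks by √(17/21), so d is multiplied by √(21/17) = 1.111. An observed d of 0.72 becomes 0.72 × 1.111 = 0.80 and is labelled large.

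**By number absent per arm (22 randomised):**

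| Absent per arm | t multiplied by | True type I error |
|---|---|---|
| 0 | 1.000 | 0.050 |
| 1 | 1.049 | 0.061 |
| 2 | 1.103 | 0.075 |
| 3 | 1.162 | 0.091 |
| 4 | 1.229 | 0.110 |
| 5 | 1.303 | 0.131 |

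At exactly 20% missing, the large-sample value is 2 × P(Z > 1.96 × 0.8) = 0.117. Simulated random 20% loss from 22 per arm gives 0.122.

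**Simulation under the null, 4 absent per arm, missing completely at random.**

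- Normal scores, SD 1.4, 20,000 trials: t-test 0.108, Welch 0.108, Mann-Whitney 0.142. Attendees only: t-test 0.050, Mann-Whitney 0.046.
- Scores rounded to a 0–10 scale, separate runs: t-test 0.105 to 0.113, Mann-Whitney 0.127 to 0.139. Attendees only: t-test 0.049 to 0.052.
- Random 20% loss, normal scores: Mann-Whitney 0.168.

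**Illustration with the planning values.** Suppose 18 attendees per arm show exactly "the mean quiz scores were 7.0 (SD 1.4) and 6.0 (SD 1.4) for the PlayMed and control cohorts".

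- Attendees only: SE = 1.4 × √(2/18) = 0.467, t = 2.14 on 34 df, p = 0.039. The 95% CI is 1.0 ± 2.032 × 0.467 = 0.05 to 1.95, and d = 1/1.4 = 0.71.
- After imputing 4 per arm: SD = 1.4 × √(17/21) = 1.260, SE = 1.260 × √(2/22) = 0.380, t = 2.63 on 42 df, p = 0.012. The 95% CI is 1.0 ± 2.018 × 0.380 = 0.23 to 1.77, and d = 1/1.260 = 0.79.

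The estimate is the same, but the p-value is less than a third as large and the interval is about a fifth narrower.

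**The case against.** The rule keeps everyone randomised in the analysis, and a second analysis is pre-specified beside it. The 20% is only a planning figure: with full attendance there is no error, and with one absence per arm it is 6.1%. Analysing attendees alone is not automatically right either. It holds the 5% level only if attendance is unrelated to performance, and disengaged participants may skip the assessment. Multiple imputation would add little, because the plan describes no baseline score to impute from.

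Much of this is fair as a limit on the claim. The inflation occurs only where someone is absent, and the attendee analysis needs an assumption about missingness. It is also an inference that the per-protocol analysis amounts to complete cases: section 4.3 sets no minimum use, but does not say how missing scores or other deviations are handled in it.

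None of it defends the imputation. The imputed point estimate equals the attendee estimate, so it has the same bias if absence depends on performance, and it understates the variance as well. Keeping everyone in the denominator preserves intention-to-treat in name only. A sensitivity analysis cannot repair the p-value that the plan designates as primary.

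**Conclusion.** The concern holds, and the rule must be changed. At 22 randomised and 18 assessed per arm, the nominal 5% t-test rejects a true null 11.0% of the time, interval coverage is about 89%, and Cohen's d is inflated by 11%. For Mann-Whitney the simulated error rate is about 13% to 14%. These figures are per comparison, two-sided, under a true null with scores missing completely at random and equal losses in the two arms. They do not depend on the assumed SD, effect or power. At a full 20% loss the t-test figure is about 12%, so 11% does not overstate the problem.

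**What to change.** Replace the imputation sentence in section 4.3 with wording such as: *The primary analysis includes all randomised participants who attended assessment, analysed in the arm to which they were allocated, with no imputed scores.* State the missing-data assumption that goes with it, and report attendance by arm.

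Define the per-protocol set. If it has no criterion beyond attendance, it duplicates the new primary analysis and should be renamed or dropped.

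If an analysis of all randomised participants is wanted, add it as a sensitivity analysis: multiple imputation combined by Rubin's rules, with arm (and job, in the staff studies) in the imputation model, plus a version that shifts the imputed mean by a range of deltas. The delta version is the more useful part, since it tests whether conclusions survive if absentees would have scored differently. Before job is used, section 3.4 needs reconciling: it attaches the job stratum to staff in studies 2A and 2B, although 2A enrols students.

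The cost is SAP wording only. P-values will be larger and intervals wider than under the current rule. No new data are needed.
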